## **SYNOPSIS AND SCHEDULE OF EVALUATIONS**

CLINICAL STUDY SYNOPSIS: Study RAP-MD-03	
Study Number	RAP-MD-03
Title of Study	A Randomized, Double-blind, Placebo-controlled, Multicenter Study of Rapastinel as Adjunctive Therapy in Major Depressive Disorder
Study Centers (Country)	Approximately 35 study centers (United States)
Development Phase	3
Objective	To evaluate the efficacy, safety, and tolerability of rapastinel adjunctive to antidepressant therapy (ADT) in patients with major depressive disorder (MDD) who have a partial response to ADT
Methodology	Multicenter, randomized, double-blind, placebo-controlled, parallel-group, 3-week study in patients with MDD who have a partial response to ongoing ADT
Number of Patients	Approximately 360 planned to be enrolled
Diagnosis and Main Criteria for Inclusion	
 
Male and female outpatients who are 18 to 65 years of age
 
Meet Diagnostic and Statistical Manual of Mental Disorders, Fifth Edition (DSM-5) criteria for MDD with a current major depressive episode of at least 8 weeks and not exceeding 18 months in duration at Visit 1
 
Have no more than partial response (< 50% improvement) to ongoing treatment with a protocol-allowed ADT
 

Test Product, Dosage, and Mode of Administration	Rapastinel (450 mg weekly intravenous [IV] administration) adjunctive to ongoing ADT, prefilled syringe

Duration of Treatment	Up to 14 days of screening and washout period, followed by a 3-week double-blind treatment period, followed by a 1-week safety follow-up period
Reference Therapy, Dosage, and Mode of Administration	Placebo adjunctive to ongoing ADT, weekly IV administration, prefilled syringe
Criteria for Evaluation	
Primary Endpoint	Change from baseline in MADRS total score at end of study
Key Secondary Endpoint	Change from baseline in MADRS total score 1 day after the first dose of randomized treatment
	
	
Pharmacokinetic Sampling	Optional: sparse pharmacokinetic (PK) samples will be taken from consented patients to determine plasma concentrations of rapastinel using a validated bioanalytical method.
Safety Measures	Adverse event (AE) recording, clinical laboratory measures, vital sign parameters, electrocardiograms (ECGs), and physical examinations
	

Statistical Methods	
The primary efficacy parameter will be the change from baseline in MADRS total score at end of study. The primary analysis will be performed using a mixed-effects model for repeated measures (MMRM) with terms for treatment, pooled study center, visit, and treatment-by-visit interaction as the fixed effects, and baseline MADRS total score, baseline MADRS total score-by-visit as covariates. The key secondary efficacy parameter, change from baseline in MADRS total score 1 day after randomized treatment will be analyzed using the same MMRM model as was used for the primary efficacy parameter. An unstructured covariance matrix will be used to model the covariance of within-patient scores. Baseline will be defined as the last measurement prior to the first dose of double-blind treatment. To control the overall type I error rate for both the primary and key secondary endpoint, a sequential testing procedure will be implemented.
 
All safety parameters will be analyzed using descriptive statistics. Safety analyses will be based on the Safety Population, defined as all randomized patients who receive at least 1 dose of randomized treatment. Efficacy analyses will be based on the modified Intent-to-Treat (MITT) Population, defined as all patients who are randomized and receive at least 1 dose of treatment and have at least 1 postrandomization assessment of the MADRS total score.

3.0	TABLE OF CONTENTS	
1.0	TITLE PAGE .....	1
2.0	SYNOPSIS AND SCHEDULE OF EVALUATIONS .....	2
3.0	TABLE OF CONTENTS.....	7
	LIST OF FIGURES .....	9
4.0	LIST OF ABBREVIATIONS .....	10
5.0	ETHICAL CONSIDERATIONS .....	12
5.1	Institutional Review Board and Independent Ethics Committee .....	12
5.2	Ethical Conduct of the Study .....	12
5.3	Patient Information and Informed Consent.....	12
6.0	INVESTIGATORS AND STUDY ADMINISTRATIVE STRUCTURE .....	13
7.0	INTRODUCTION .....	14
8.0	STUDY OBJECTIVES.....	18
9.0	INVESTIGATIONAL PLAN .....	20
9.1	Overall Study Design and Plan: Description .....	20

**4.0****LIST OF ABBREVIATIONS**

ADT	antidepressant therapy
AE	adverse event
ALT	alanine aminotransferase
ANCOVA	analysis of covariance
AST	aspartate aminotransferase
ATRQ	Antidepressant Treatment Response Questionnaire
BMI	body mass index
BP	blood pressure
[REDACTED]	[REDACTED]
[REDACTED]	[REDACTED]
CFR	Code of Federal Regulations
[REDACTED]	[REDACTED]
CI	confidence interval
[REDACTED]	[REDACTED]
[REDACTED]	[REDACTED]
DSM-5	Diagnostic and Statistical Manual of Mental Disorders, Fifth Edition
DSST	Digit Symbol Substitution Test
DxV	Diagnostic Validation Questionnaire
ECG	electrocardiogram, electrocardiographic
eCRF	electronic case report form
ECT	electroconvulsive therapy
EDC	electronic data capture
[REDACTED]	[REDACTED]
ET	early termination
FDA	Food and Drug Administration
FR	Federal Register
GCP	good clinical practice
HIPAA	Health Insurance Portability and Accountability Act of 1996
ICF	informed consent form

ICH	International Conference on Harmonisation of Technical Requirements
IND	Investigational New Drug (application)
IP	investigational product
IRB	Institutional Review Board
ITT	Intent-to-Treat
IV	intravenous
IWRS	interactive web response system
MADRS	Montgomery-Asberg Depression Rating Scale
MDD	major depressive disorder
MMRM	mixed-effects model for repeated measures
NMDAR	N-methyl-D-aspartate receptor
PCS	potentially clinically significant
PID	patient identification
QTc	QT interval corrected for heart rate
QTcB	QT interval corrected for heart rate using the Bazett formula ( $QTcB = QT/[RR]^{1/2}$ )
QTcF	QT interval corrected for heart rate using the Fridericia formula ( $QTcF = QT/[RR]^{4/5}$ )
SAE	serious adverse event
SAP	Statistical Analysis Plan
SCID	Structured Clinical Interview for Diagnostic Statistic Manual of Mental Health Disorders, Fifth Edition
SD	standard deviation
████████	████████
SDMT	Symbol Digit Modalities Test
SNRI	selective serotonin and norepinephrine reuptake inhibitor
SSRI	selective serotonin reuptake inhibitor
TEAE	treatment-emergent adverse event
UDS	urine drug screen
ULN	upper limit of normal

**5.0****ETHICAL CONSIDERATIONS****5.1****INSTITUTIONAL REVIEW BOARD AND INDEPENDENT ETHICS COMMITTEE**

Approval by the Institutional Review Board (IRB) before the start of the study will be the responsibility of the Investigator. A copy of the approval letter will be supplied to the Sponsor, along with a roster of IRB members or the US Department of Health and Human Services general assurance number. During the course of the study, the Investigator will provide timely and accurate reports to the IRB on the progress of the study, at intervals not exceeding 1 year (or as appropriate), and will notify the IRB of serious adverse events (SAEs) or other significant safety findings. The study protocol, informed consent form (ICF), information sheet advertisements, and amendments (if any) will be approved by the IRBs at the study centers in conformance with the US CFR, Title 21, Part 56.

**5.2****ETHICAL CONDUCT OF THE STUDY**

This clinical study will be conducted in accordance with the ethical principles that have their origins in the Declaration of Helsinki.

This clinical study will comply with the ICH Guidance on General Considerations for Clinical Trials (ICH-E8; 62 FR 66113, 17 Dec 1997) and GCP (ICH-E6; 62 FR 25692, 09 May 1997), as well as Part 312 of the US CFR.

**5.3****PATIENT INFORMATION AND INFORMED CONSENT**

After being given an explanation of the study and before participating in any study procedures, each patient must provide written informed consent in compliance with 21 CFR, Parts 50 and 312 and give HIPAA authorization.

Each patient will read and sign an ICF and/or other authorization form as per local regulations; each patient will be made aware that he or she may withdraw from the study at any time.

The ICF contains all the elements of informed consent listed in [Appendix I](#) of this protocol. Signed copies of the ICF and the HIPAA or other locally applicable form will be given to the patient, and both documents will be placed in the Investigator's study files.

**6.0****INVESTIGATORS AND STUDY ADMINISTRATIVE STRUCTURE**

This study will be performed at approximately 35 study centers in the United States.

The Investigator is responsible for ensuring that the investigation is conducted according to the signed Investigator statement, the investigational plan, GCP guidelines, and applicable regulations; for protecting the rights, safety, and welfare of patients under the Investigator's care; and for the control of investigational products under investigation. An investigator shall obtain the informed consent for each patient prior to the patient enrolling in the study and/or prior to participating in any study-related activity.

The Investigator at each study center must meet his or her obligations to the patients, ethics committee, Sponsor, and regulatory authorities by maintaining oversight and control of the study's conduct and the study staff. It is the responsibility of the Investigator to ensure that any and all delegated duties be assigned to qualified staff by education, experience, and licensure (in accordance with local regulations) and that the Investigator oversight is documented and assessment of staff capabilities and performance is consistent with the study investigational plan. The Investigator at each study center will be responsible for the management of the study, including maintaining the study file and the patient records, corresponding with the IRB, and completing the electronic case report forms (eCRFs).

## **7.0 INTRODUCTION**

### *Disease Burden of Major Depressive Disorder*

Major depressive disorder (MDD) is a highly disabling, serious condition which is associated with significant morbidity and mortality. MDD manifests as a major depressive episode (which may be singular or recurrent) in which the affected individual experiences 1) depressed mood, or 2) loss of interest or pleasure (as well as other symptoms) for most of the day, nearly every day, for at least 2 weeks. MDD affects approximately 14.8 million American adults, or about 6.7% of the US population 18 years of age and older, in a given year (Kessler et al, 2005). Worldwide, about 15% of the adult population is at lifetime risk of developing MDD (Kessler et al, 1994).

Depression may cause serious, long-lasting symptoms and often disrupts a person's ability to perform routine tasks. In 2000, unipolar depressive disorders were by far the leading cause (11.9%) of worldwide years of life lived with disability (World Health Organization, 2001), and the total economic burden of treating depression in the United States was \$83.1 billion, with workplace costs, including missed days and lack of productivity due to illness, accounting for most of the total economic burden (62%). Other economic burdens in 2000 included \$26.1 billion (31%) for treatment costs and \$5.4 billion (7%) for suicide-related costs (Greenberg et al, 2003).

MDD is a leading cause of disability in the United States (Murray et al, 2013). Moreover, MDD is known to be a significant risk factor for suicide and ischemic heart disease, as it accounted for 16 million of the disability adjusted life years (DALYs) associated with suicide and 4 million of the DALYs associated with ischemic heart disease. Research has shown that untreated depression has both a functional (social and work role) as well as a neuroanatomical (hippocampal shrinkage) effect on the patient (Videbech and Ravnkilde, 2004). Given the disease burden and link to suicidality as well as increased mortality with other comorbid conditions, MDD is a serious and life-threatening condition which is a leading cause of disability in the world.

### *Selective Serotonin Reuptake Inhibitors and Selective Serotonin and Norepinephrine Reuptake Inhibitors in Major Depressive Disorder*

Selective serotonin reuptake inhibitors (SSRIs) and selective serotonin and norepinephrine reuptake inhibitors (SNRIs) currently represent the first line of treatment of depression in the **United States**. Unfortunately, a large number of patients do not experience therapeutic benefit from these first-line agents (Rosenzweig-Lipson et al, 2007). Lack of sufficient response to adequate treatment remains a critical problem in the management of patients with MDD. Up to two-thirds of patients treated with first-line antidepressant monotherapy do not reach full remission, and as many as a third become treatment resistant (Fava and Davidson, 1996; Trivedi et al, 2006). Not achieving remission has been shown to be predictive of poorer psychosocial functioning, higher rates of relapse, and higher rates of rehospitalization (McIntyre and O'Donovan, 2004).

The results of the STAR\*D study suggest that with successive failures of treatment, patients are less and less likely to respond to subsequent treatment, and those who do respond are more likely to relapse (Rush et al, 2006). Present strategies available to treat patients who do not respond to first-line antidepressant monotherapy include switching of antidepressant (either within or between classes); combination therapy in which multiple antidepressants are used simultaneously; augmentation of ongoing antidepressant monotherapy with adjunctive use of drugs such as mood stabilizers or atypical antipsychotics (Boland and Keller, 2006); and nonpharmacologic treatments including psychotherapy and phototherapy, vagus nerve stimulation, transcranial magnetic stimulation, and electroconvulsive therapy (ECT). Clearly, there remains a critically important unmet medical need for this patient population.

Existing antidepressants have a number of limitations, leading to considerable unmet medical need in the effective treatment of MDD, with up to 50% of patients with MDD having an inadequate response or failing current antidepressant therapy (ADT). Currently available first-line antidepressants (SSRIs, SNRIs) typically take 3 to 4 weeks or more of continuous daily dosing to relieve symptoms of MDD and are associated with side effects related to their pharmacological mechanisms of action (sexual dysfunction, weight gain, jitteriness, sleep disturbances), which are further associated with poor patient compliance (Masand 2003, Ashton et al, 2005). Patients often experience undesirable side effects before they experience an improvement in depressive symptoms, which could lead to premature discontinuation of therapy. Taken together, these factors define significant areas for improvement of ADT.

Patients vary greatly in their response to antidepressants and it is not possible to reliably predict whether an individual patient will respond to a given antidepressant. This leads to clinicians often using a trial-and-error approach to identify an effective antidepressant. Due to the gradual development of the full therapeutic effect of currently available antidepressants, each antidepressant needs to be administered for 4 weeks or longer in order to determine the individual therapeutic benefit, making the process of finding an effective antidepressant a lengthy process for patients who are often severely depressed and at a high risk for suicide. Clearly a drug that could induce a rapid antidepressant effect would represent a major advancement for these patients.

#### *Atypical Antipsychotics as Adjunctive Therapy in Major Depressive Disorder*

The available treatments for adjunctive therapy in MDD also have substantial safety and efficacy limitations. The drugs currently approved for use as adjunctive therapy to antidepressants for the treatment of MDD—namely, the atypical antipsychotics Abilify® (aripiprazole), Seroquel XR® (quetiapine fumarate), and Rexulti® (brexpiprazole)—are associated with significant adverse reactions, as well as a number of serious warnings and precautions. Originally developed for the treatment of psychotic disorders, these drugs share a number of clinically relevant adverse effects based on their mechanisms of action.

As all current antipsychotic agents modulate central dopaminergic systems, they all carry a risk of extrapyramidal symptoms such as muscular rigidity, acute dystonia, as well as akathisia, which is a particularly relevant adverse event (AE) that complicates clinical management in a significant number of treated individuals, as high as 45% (Sachdev, 1995). In addition, these compounds are associated with a risk of neuroleptic malignant syndrome and tardive dyskinesia. Depending on their individual pharmacological profile, antipsychotics also carry a risk for metabolic changes including hyperglycemia/diabetes mellitus, dyslipidemia and body weight gain; blood dyskrasias such as leucopenia, neutropenia, and agranulocytosis; orthostatic hypotension; cognitive and motor impairment; cataracts; and insomnia (Abilify, 2014; Seroquel, 2013; Rexulti, 2015). The range of clinically relevant side effects with antipsychotics has to be balanced carefully against the potential for therapeutic benefits in patients with major depression. In this context it is important to highlight that for the approved atypical antipsychotics the full therapeutic benefit required several weeks of daily adjunctive dosing to become apparent, and in many subjects adverse effects occurred substantially earlier than the mood-alleviating effects of these drugs.

Furthermore, the drugs currently approved for adjunctive treatment of MDD also have limited efficacy. The pivotal studies for Abilify, the atypical antipsychotic most commonly used for adjunctive treatment of MDD, showed a delayed onset of effect (1-2 weeks), a modest magnitude of effect (effect sizes were 0.35-0.39 after 6 weeks of repeat dosing) and modest rates of response and remission after 6 weeks of repeat dosing (response rates were 32-34% and remission rates were 25-26%) (Berman et al, 2007; Marcus et al, 2008).

Clearly, there is a substantial need for the development of novel treatments with a better safety/tolerability profile and a faster onset of full therapeutic benefit. Rapastinel has initially shown substantially improved safety/tolerability as well as promising efficacy, in both speed of onset and overall magnitude, for adjunctive therapy in MDD.

#### *Rapastinel as a Novel Approach to Major Depressive Disorder Treatment*

The mechanism of action of rapastinel is entirely different from that of atypical antipsychotics. Rapastinel is an N-methyl-D-aspartate receptor (NMDAR) modulator with a novel and complex pharmacological mechanism of action, acting as a nonselective agent at NR2 subunits and displaying properties as a functional partial agonist in a number of pharmacological assays.

Rapastinel has demonstrated antidepressant properties in relevant animal models, displays cognitive enhancing properties in treated animals, and facilitates hippocampal long-term potentiation of synaptic transmission in preclinical models. In contrast to ketamine, no signal of abuse liability was detected in informative animal models.

Rapastinel is available as an intravenous (IV) formulation only. In 2 Phase 2 clinical studies in patients with MDD, single IV doses of rapastinel 5 mg/kg and 10 mg/kg have been shown to produce marked antidepressant effects within 1 day that lasted for approximately 1 week or longer in responding patients. These antidepressant effects are very similar to ketamine's effects when administered at a low dose as an infusion. In a systematic review and meta-analysis of ketamine and other NMDAR antagonists in the treatment of major depression, a single infusion of ketamine produced a rapid, yet transient antidepressant effect, accompanied by brief psychotomimetic and dissociative effects ([Newport et al, 2015](#)).

The available Phase 1 and 2 data demonstrated a favorable safety and tolerability profile of rapastinel. In contrast to ketamine, rapastinel has not shown a high likelihood to induce psychotomimetic or dissociative effects in humans so far.

The purpose of this study is to prospectively confirm that rapastinel, when administered as an adjunctive treatment at a dose of 450 mg as a short IV infusion in patients with MDD, is significantly superior to placebo in rapidly reducing depressive symptoms. Furthermore, the safety and tolerability of rapastinel will be investigated. The study is intended to support an application for regulatory approval of rapastinel as adjunctive treatment for MDD.

## **8.0 STUDY OBJECTIVES**

The objectives of this study are to evaluate *the* efficacy, safety, and tolerability of rapastinel adjunctive to ongoing ADT in patients with MDD who have a partial response to ADT.

### **Efficacy Objectives**

- **Primary efficacy objective:** To evaluate the efficacy of rapastinel (450 mg IV) versus placebo in the treatment of MDD as an adjunct to ongoing ADT, as measured by the change from baseline *to end of study* in the Montgomery-Asberg Depression Rating Scale (MADRS) total score.
- **Key secondary efficacy objective:** To evaluate the efficacy of rapastinel (450 mg IV) versus placebo in the treatment of MDD as an adjunct to ongoing ADT, as measured by the change from baseline *in the* MADRS total score *1 day after first dose of treatment.*

[REDACTED]

[REDACTED]

[REDACTED]

[REDACTED]

[REDACTED]

[REDACTED]

[REDACTED]

[REDACTED]

[REDACTED]

A 9x9 grid of black bars on a white background. The bars are arranged in a pattern where the width of each bar in a row is the sum of the widths of the bars in the row above it. The widths of the bars in each row are: Row 1: 1, 2, 3, 4, 5, 6, 7, 8, 9. Row 2: 1, 2, 3, 4, 5, 6, 7, 8, 9. Row 3: 1, 2, 3, 4, 5, 6, 7, 8, 9. Row 4: 1, 2, 3, 4, 5, 6, 7, 8, 9. Row 5: 1, 2, 3, 4, 5, 6, 7, 8, 9. Row 6: 1, 2, 3, 4, 5, 6, 7, 8, 9. Row 7: 1, 2, 3, 4, 5, 6, 7, 8, 9. Row 8: 1, 2, 3, 4, 5, 6, 7, 8, 9. Row 9: 1, 2, 3, 4, 5, 6, 7, 8, 9.

**9.0****INVESTIGATIONAL PLAN****9.1****OVERALL STUDY DESIGN AND PLAN: DESCRIPTION**

This study is a multicenter, randomized, double-blind, placebo-controlled, parallel-group, 3-week study in patients with MDD who have a partial response to ADT. The study will include a total of 12 visits and will be approximately 4 to 6 weeks in duration (Figure 9.1-1):

- Up to 2-week screening period
- 3-week double-blind treatment period
- 1-week safety follow-up period (for patients who do not enter the RAP-MD-04 maintenance study)

**9.1.1****Screening Period**

After providing written consent, patients will enter a screening period of up to 14 days. The screening/washout period will be up to 2 weeks prior to Visit 2. Screening procedures may be conducted on up to 2 separate dates where necessary to accommodate patient and study center schedule; however, every effort should be made to conduct all procedures as early as possible in the screening period and the rater-administered MADRS and computer-administered MADRS must be collected on the same date. Patients will not receive any investigational product (IP) during the screening period but must continue their background ADT at the same dose. Patients meeting the eligibility criteria at the end of Visit 2 (Baseline) will be assigned a treatment by the interactive web response system (IWRS) and enter the double-blind treatment period.

**9.1.2****Double-blind Treatment Period**

Approximately 700 patients are planned for enrollment in the double-blind treatment period (350 patients each in the rapastinel 450 mg and placebo groups). Patients will be randomized in a ratio of 1:1 to 1 of 2 treatment groups: rapastinel 450 mg IV weekly or placebo IV weekly (both adjunctive to ongoing ADT).

During the double-blind treatment period, patients will have 3 study visits per week. The visits will occur in the following pattern: treatment day, 1 day following the treatment day, 4 days following the treatment day, and 7 days following the treatment day (which is the next treatment day). If necessary, study visits may be conducted up to 2 days before or after the scheduled visits with the exception of visits that are 24 hours apart (eg, Visits 2 and 3 must be conducted 1 day apart; similarly, Visits 5 and 6 as well as Visits 8 and 9 must be conducted 1 day apart). All patients who receive IP must complete Visit 11. Upon completion of the double-blind treatment period, patients are eligible to enter the RAP-MD-04 maintenance study. Patients who do not enter RAP-MD-04 will enter a 1-week safety follow-up period.

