### 9.7.9 Determination of Sample Size

**The originally proposed primary efficacy variable is the change from baseline in the MADRS total score at 1 day after the first dose of treatment. The study was planned to randomize 700 patients assuming SD of 10 points, which provides 99% power to detect a difference of 3.25 points in MADRS total score between rapastinel 450 mg and placebo at a 2-sided significance level of 0.05.**

**While the study was ongoing, various feedbacks were received from the regulatory agencies including the FDA, EMA, and the Japanese regulatory agency. Following the feedbacks, the primary efficacy variable was revised to be the change from baseline in MADRS score at the last visit, Day 21, and included in Amendment 2 of the protocol. At the same time of Amendment 2, a blinded data review was conducted for Studies RAP-MD-01, RAP-MD-02, and RAP-MD-03. The pooled SD for the 3 studies were 7.4, 8.0, and 8.7, respectively, all smaller than the originally assumed 10 points. Sample size was re-calculated using 8.7 as the common SD. The calculation used MMRM model with simulations; it also assumed correlation of 0.5 between the repeated measures and an overall drop-out rate of 15%. To have 90% power, the total sample size required is 360 patients. However, the study had already enrolled more than 390 patients with less than 5% of overall drop-out rate, surpassing the re-estimated sample size of 360 patients. The study enrollment was halted as soon as operationally feasible. The final sample size is approximately 420 patients (210 patients per treatment group).**

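### Protocol 9.1.2 still plans about 700 patients and the synopsis about 360, while protocol 9.7.9 and SAP 12.0 give a final size of about 420

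*Protocol*

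**What the plan says.** **Protocol 9.1.2 (Double-blind Treatment Period):** "Approximately 700 patients are planned for enrollment in the double-blind treatment period (350 patients each in the rapastinel 450 mg and placebo groups". The sentence describes a current plan and carries no note that it has been replaced.

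**Protocol synopsis, Number of Patients:** "Approximately 360 planned to be enrolled".

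**Protocol 9.7.9 (Determination of Sample Size)** gives the history in order:
- Original design, for the 1-day endpoint: "The study was planned to randomize 700 patients assuming SD of 10 points". The power claimed for that design is 99%, for a 3.25-point difference tested at the two-sided 5% level.
- Change of endpoint: "the primary efficacy variable was revised to be the change from baseline in MADRS score at the last visit, Day 21".
- Re-estimation with a standard deviation of 8.7 and 15% overall dropout: "To have 90% power, the total sample size required is 360 patients".
- Status at that time: "However, the study had already enrolled more than 390 patients with less than 5% of overall drop-out rate".
- Consequence: "The study enrollment was halted as soon as operationally feasible". The section closes with a final size of about 420, which is 210 in each group.

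**SAP 12.0** tells the same story and ends on the same 420 (210 per group). It differs in splitting the 15% dropout into 5% during the placebo lead-in and 10% after randomization.

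**The concern.** Planned size is a basic design figure, and readers such as ethics committees, investigators and report writers often take it from the synopsis or the design section. Here both of those places disagree with the sample size section of the same protocol, and with each other.

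The two conflicts differ in kind. The 700 in 9.1.2 is a figure that 9.7.9 itself describes as superseded. The 360 in the synopsis is a live number, because it is the re-estimated requirement. It is, however, worded as the number planned for enrolment in a protocol that reports enrolment already beyond it. Someone using either section alone would report the wrong trial size. Someone comparing 700 with about 420 could also suspect an unexplained early stop, although 9.7.9 explains the change.

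**Working it through.** **1. The plan's own original figure.** Inputs from 9.7.9: 350 per arm, SD 10, difference 3.25, two-sided 0.05. Two-sample normal approximation:

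power = Φ( 3.25 / (10 × √(2/350)) − 1.960 ) = Φ( 3.25/0.7559 − 1.960 ) = Φ(2.339) = 0.990.

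This matches the stated 99%. The 700 was therefore correctly calculated for the original 1-day design; what is wrong is that 9.1.2 still presents it as the plan.

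**2. The figures side by side.**

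| Place | Total | Per arm | Status given there |
|---|---|---|---|
| Protocol 9.1.2 | about 700 | 350 | current plan |
| Synopsis | about 360 | not stated | current plan |
| Protocol 9.7.9, SAP 12.0 | 700 | not stated | original plan |
| Protocol 9.7.9, SAP 12.0 | 360 | not stated | requirement for 90% power |
| Protocol 9.7.9, SAP 12.0 | more than 390 | not stated | already enrolled |
| Protocol 9.7.9, SAP 12.0 | about 420 | 210 | final size |

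**3. Size of the differences.**
- 9.1.2 against the final size: 210/350 − 1 = −40%, or 140 fewer patients per arm. Both are counts per treatment group, so the comparison is direct.
- Synopsis against the final size: 420/360 − 1 = +17%.
- Synopsis against the number already enrolled: 390/360 − 1 = +8%. The text says more than 390, so this is a lower bound.
- Counting base: with the SAP's dropout split, 360 may be counted at lead-in entry. Then 360 × 0.95 = 342 would be randomized, and 420/342 − 1 = +23%. The 17% therefore assumes the same base for both numbers.

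**4. Could a different meaning of enrolled reconcile 360 with 420?** Protocol 9.7.1.1 counts patients who consent, receive an identification number and enter screening. SAP 4.1 also requires a dose of double-blind product, and the SAP's double-blind period includes the placebo lead-in. Under either definition, those enrolled are at least as many as those randomized. An enrolment of 360 cannot supply 210 patients to each of two groups.

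**5. Is there a power shortfall?** This can be answered without knowing the treatment difference behind the 360. Expected completers:
- Requirement, with 15% dropout: 360 × 0.85 = 306.
- Final size, same dropout: 420 × 0.85 = 357.
- Final size at 5% dropout, the upper limit of what 9.7.9 reports so far: 420 × 0.95 = 399.
- SAP split, with 360 counted at lead-in entry and 420 at randomization: 360 × 0.95 × 0.90 = 308 against 420 × 0.90 = 378.

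On every base the final size leaves more completers than the number the sponsor's simulation found sufficient for 90% power.

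**The case against.** The strongest reply is that the documents already explain every figure. Section 9.7.9 sets out 700, 360, more than 390 and 420 in sequence, and SAP 12.0 repeats it. Enrolment had been halted, so the stale 700 could not change recruitment, and no population, model or testing rule uses it. A requirement of 360 and a final count of 420 are also different quantities and need not be equal. All of this stands, and it limits the point to a text correction. It does not make 9.1.2 right. That sentence is in the current body of the protocol and not in a summary of changes. Keeping the lead-in from study centers cannot explain it either, because 9.7.9 of the same protocol discloses both 360 and 420. Nor does it rescue the synopsis wording, which plans an enrolment that had already been passed.

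Three stronger readings are tempting, and the documents support none of them.
- **The trial is underpowered because it stopped far below 700.** The 700 belonged to an SD of 10 and 99% power for the former endpoint. The final size exceeds the re-estimated requirement.
- **The trial stopped early without explanation.** Protocol 9.7.8 and 9.7.9 describe a blinded review of the SD, a re-estimation and a halt to enrolment.
- **The 360 is unsupported because no Day 21 difference is stated.** The SAP introduction says that it also elaborates a Restricted Access Addendum, which is not among the documents reviewed and may state it. Approximation cannot settle the matter. If 3.25 was carried over (an assumption), completers per arm = 2 × (1.960 + 1.282)² × SD²/3.25². With SD 8.7 this is 151 per arm, and 302/0.85 gives 356 in total. If the 0.5 correlation also applies to baseline (a further assumption), the SD is 8.7 × √0.75 = 7.53, which needs 113 per arm, and 226/0.85 gives 266. The agreement with 360 depends on the approximation, so it neither confirms nor refutes the figure.

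**Conclusion.** The inconsistency is real and should be corrected. Section 9.1.2 states a superseded size: the final 210 per arm is 40% below its 350. The synopsis presents the re-estimated requirement as planned enrolment when more than 390 patients were already in; the final 420 is 17% above it on the same counting base, or 23% above it if 360 was counted at lead-in entry and 420 at randomization.

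The point goes no further than the stated size. There is no shortfall against the sponsor's own requirement and no effect on the analysis. The statement on power takes the sponsor's 360 as given; it does not verify the simulation behind it. That the 700 was simply missed when 9.7.9 was rewritten is a reasonable inference, but the documents do not say so.

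**What to change.** - **Protocol 9.1.2:** replace 700 (350 per arm) with the final size in 9.7.9, about 420 patients, 210 per treatment group.
- **Protocol synopsis:** state the final size of about 420. If 360 is kept, label it as the re-estimated requirement for 90% power.
- **Protocol 9.7.9 and SAP 12.0:** leave as they stand. They already identify 700 as the original plan and 360 as the requirement.

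The cost is two text corrections. They go through the amendment process in protocol 9.9, which calls for IRB approval and signed investigator pages before implementation, so they are best included in an amendment made for other reasons. No patients are added and no analysis changes.
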